5.2 Study Analysis, Sample Size and Pooling of Data

Study Analysis:

The primary efficacy analysis of this study is to compare the mean change in hair count change from baseline to 16-weeks following the initial application at baseline of REVIAN to the SHAM. This will be performed using mixed effects analysis of covariance (ANCOVA) where baseline characteristics and demographics may be considered as covariates. Comparison between active groups will not be tested for statistical significance as the study is not powered for these comparisons. Instead, each active will be compared to the SHAM individually. Details on adjustments for multiple testing to a single SHAM will be provided in a statistical analysis plan.

Power Calculation, Sample Size:

Prior hair growth studies, regardless of potential efficacy of the SHAM device, showed the delta between active treatments and control treatments was consistently at around 15-22 hairs/cm² which appears to be the expected level of improvement. It is estimated that participants in the active group will have greater than 15 hairs/cm² by 16-weeks. The study design is a parallel arm study of superiority of PhotonMD devices to SHAM with a minimum of 40 participants per arm. Assumptions are 15 hair difference between treatments, standard deviation (SD)=20, 10% dropout rate, 5% alpha level, 90% power and 2-sided t-test.

The study will accrue a total of 200 participants (50 per each Active Study Arm and 50 control participants) to make sure, after lost to follow-up, that there is a minimum of 160 evaluable (40 per arm) participants.

Pooling of Data:

The clinical study will be conducted under a common protocol for each of 3 investigational sites with the intention of pooling the data over all sites for analysis. Every effort will be made to promote consistency in study execution at each investigational site.

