3. STUDY DESIGN

This study is designed as a prospective, randomized, controlled, double-blind, four-arm study. Up to 3 clinical sites will enroll up to 200 participants over an approximate 6-month duration. Eligible participants with AGA meeting all inclusion and exclusion criteria will be enrolled and randomized to one of four study arms in a 1:1:1:1 ratio:

- Arm 1: Active *REVIAN* 101 (___mW/cm² of 625 nm and 660 nm)
- Arm 2: Active *REVIAN* 102 (____mW/cm² of 425 nm)
- Arm 3: Active *REVIAN* 103 (____mW/cm² of 425 nm + ___mW/cm2 of 625 nm and 660 nm)
- Arm 4: Non-Active *REVIAN* Cap 100 (SHAM)

Male and female participants will be randomized from separate randomization schedules to ensure balance among treatment arms in each gender.

All data except for Global Assessment Photography and Macrophotography will be captured in an electronic clinical report form (eCRF). Global Assessment Photography and Macrophotography data will be imported from external vendor. Demographic, baseline characteristics, efficacy and safety data will be collected at regularly scheduled visits according to the planned schedule of procedures (Table 1).

Screening procedures will be performed at Visit 1.

Participants who are eligible to enroll will return within 7 days for Visit 2 to obtain baseline data and to be randomized to one of the treatment arms. The first treatment will be performed in the clinic on Visit 2.

Visit 3 will occur approximately 7 days later via telephone interviews to assess treatment compliance, to report use of concomitant medications and to report any adverse events.

Visits 4 and 5 will occur approximately 8 and 16 weeks, respectively, after Visit 1. Participants will return to the investigation centers for efficacy assessments and questionnaires.

The final visit (Visit 6) will occur approximately 10 weeks after Visit 5. Participants will undergo a final assessment of efficacy and safety at Visit 6. Participants will return the caps at Visit 6. If there are no adverse events requiring follow-up, participants will not need to return for any follow up assessments.

Any participant who competes the Week 16 efficacy assessments (at Visit 5) will be considered a completer.

Visit 1	Visit 2	Visit 3	Visit 4	Visit 5	Visit 6
Screening (Day -7)	Baseline (Day 0)	Phone Call (7 ±3 Days)	Week 8 ^{1,2} (56 ±5 Days)	Week 16 ^{1,2} (112 ±10 Days)	Week 26 ^{1,2} (182 ±10 Days)
X	Х				
X					
Х					
X					
X	Х				
X	Х				
	Х				Х
	Х				
	Х		Х3	X ³	X ³
	Х		Х	Х	Х

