8.2. Hypothesis Testing

The treatment consists of 3 active caps and one Sham cap. Each active cap group will be compared to the same Sham group using 1 degree of freedom contrasts in general linear models analysis of covariance (ANCOVA). Comparisons will be adjusted for multiple comparisons to the same Sham group using Dunnett's correction.

The primary outcome is the change from baseline in hair count after 16 weeks of treatment with a cap. The null hypothesis is there is no difference in outcome between an active cap compared to a Sham cap, while the alternative hypothesis is there is a difference outcome between active compared Sham cap:

 H_{null} : $D_{active} = D_{Sham}$

 $H_{alternative} \text{: } D_{active} \neq D_{Sham}$

The null hypothesis will be rejected in favor of the alternative hypothesis for each active cap if the Dunnett's corrected p-value for the contrast ≤ 0.05 . Treatment superiority will be

demonstrated if the significant difference is in favor of the active cap (e.g., greater increase in hair count for the active cap. No comparisons between active caps will be performed.

Secondary outcomes will the same hypotheses testing process as the primary outcome, but with statistical methods appropriate for the type of endpoints to be tested. For example, continuous outcomes will be analysed by parametric methods, such as ANCOVA, while categorical outcomes will be analysed by non-parametric methods, such as Cochran-Mantel-Haenszel (CMH) test. Details of analyses by outcomes are provided in Section 10.

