10. EFFICACY ANALYSES

10.1. Primary Endpoint

The primary efficacy endpoint is the change from baseline in hair count, over a pre-specified 1 cm² area of scalp after 16 weeks of treatment (CFB_HC16).

As specified in Section 9.2, each active cap will be compared to the same Sham treatment using 1 degree of freedom contrasts in an analysis of covariance (ANCOVA). Analyses will be adjusted for multiple comparisons using Dunnett's correction. An example of SAS code to be used for the primary analysis is as follows:

PROC MIXED; CLASS SITE ARM; MODEL CFB_HC16 = SITE ARM SITE*ARM <covariates>; LSMEANS ARM /ADJUST=DUNNETT DIFF=CONTROL('SHAM'); RUN;

If the SITE*ARM interaction is not significant (p>0.05), this interaction will be dropped from the subsequent model. SITE will remain in the model if it significantly attributes to variability of the outcome. All subsequent analyses of secondary endpoints will retain the same factors and covariates as the primary outcome analysis.

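### SAP 8.2 and 10.1 use single-step Dunnett, which is valid; step-down Dunnett never shows fewer caps superior, keeps the 5% family-wise limit and gains power when more than one cap works

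*Combined protocol and SAP*

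**What the plan says.** Protocol 5.2 plans three cap-versus-sham comparisons and no comparison between active caps. It defers the multiplicity method to the SAP: "each active will be compared to the SHAM individually. Details on adjustments for multiple testing to a single SHAM will be provided". Nothing in that sentence is wrong, and it does not fix the rule.

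The rule is in the SAP. Section 8.2 states "Comparisons will be adjusted for multiple comparisons to the same Sham group using" Dunnett's correction, and rejects the null hypothesis for a cap when its own Dunnett-corrected p-value is at most 0.05. Section 10.1 gives PROC MIXED code with "LSMEANS ARM /ADJUST=DUNNETT" and sham as control. Neither section describes an ordering, a stepping rule or a closed test, so the procedure is single-step.

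SAP 10.2 analyses change in hair count at weeks 8 and 26, and the rate of change, in the way set for the primary endpoint.

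The design inputs in protocol 5.2 are "Assumptions are 15 hair difference between treatments", with "standard deviation (SD)=20, 10% dropout rate, 5% alpha level, 90% power and 2-sided t-test", and "a minimum of 160 evaluable (40 per arm) participants".

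**The concern.** Under single-step Dunnett, each cap must beat the critical value that protects against three null caps at once. Once one cap has been shown superior, at most two nulls can still be true, and a smaller critical value protects them at the same 5%. The planned rule does not use this.

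The trial's confirmatory result is a separate verdict on each cap. If several caps work, as the expected 15-22 hairs/cm² advantage in protocol 5.2 suggests, an effective cap is more likely to miss the primary endpoint than the 5% family-wise limit requires.

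**Working it through.** **Inputs.** Difference 15, SD 20, two-sided 5%, 90% power, and 40 evaluable per arm (protocol 5.2, SAP 5). Accrual is 50 per arm (protocol 5.2: "The study will accrue a total of 200 participants (50 per each Active Study Arm and 50 control participants"). Allocation is equal (SAP 3: "randomized to one of four study arms in a 1:1:1:1 ratio"), so any two cap-versus-sham contrasts correlate 0.5. Common SD and no precision gain from covariates are assumed.

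**1. The plan's own figure.** n = 2(z₀.₉₇₅ + z₀.₉₀)² SD²/δ² = 2 × (1.960 + 1.282)² × 400/225 ≈ 37.4, so 38 per arm. The exact t calculation gives 39. The stated 40 is reproduced, with power of 91.2% by two-sample t-test. This uses an unadjusted 5% level.

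**2. Critical values at 40 per arm** (df = 4 × 39 = 156, two-sided, correlation 0.5):

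| Comparisons still open | Critical value of \|t\| | Nominal p |
|---|---|---|
| 3 | 2.372 | 0.0189 |
| 2 | 2.232 | 0.0270 |
| 1 | 1.975 | 0.0500 |

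Single-step applies 2.372 to every cap. Step-down tests the largest |t| against 2.372, the next against 2.232 and the last against 1.975, and stops at the first failure. Any cap above 2.372 passes under both rules, so step-down never rejects fewer.

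**3. Hand check of single-step power.** The noncentrality is 15/(20 × √(2/40)) = 15/4.472 = 3.354. Power is about Φ(3.354 − 2.372) = Φ(0.98), or roughly 84%. Simulation gives 83.6%.

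**4. Simulated power** (2,000,000 trials per scenario; single-step versus step-down; each working cap gains 15 hairs):

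| Evaluable per arm | Caps that work | Per working cap | All working caps shown |
|---|---|---|---|
| 40 | three | 83.6% v 88.9% | 67.0% v 80.2% |
| 40 | two | 83.6% v 85.9% | 73.8% v 78.4% |
| 40 | one | 83.6% v 83.7% | same as per cap |
| 45 (50 less 10%) | three | 88.1% v 92.6% | 74.9% v 86.0% |
| 50 (all accrued) | three | 91.6% v 95.1% | 81.3% v 90.3% |

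The 50-per-arm row takes the effect as undiluted by carry-forward imputation.

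**5. Across the plan's effect range** (40 per arm, all caps equal, per cap): 18.5 hairs, 96.0% v 98.0%; 22 hairs, 99.4% v 99.8%. If two caps gain 22 and one gains 15, the weaker cap goes from 83.5% to 91.4%.

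**6. Showing at least one cap.** Both rules share the first step, so this chance is identical: 96.3% with three caps at 15 hairs and 40 per arm.

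**7. Family-wise error** (40 per arm, working caps at 15 hairs):

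| Null caps | Single-step | Step-down |
|---|---|---|
| three | 5.0% | 5.0% |
| two | 3.5% | 4.6% |
| one | 1.9% | 4.1% |

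With one null cap and two caps at 22 hairs, the figures are 1.9% and 4.95%.

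**The case against.** The strongest reply is that nothing here is broken. The SAP prespecifies a recognised method with full family-wise control, a clear decision rule and code that matches it. That stands: this is a matter of efficiency, and a reader who inferred that the SAP's multiplicity control is faulty would be wrong.

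Three further points also stand.

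- **The extra power is not free.** A reader might infer that single-step gives no added protection against false claims. It does: with one null cap its actual error is 1.9%, against 4.1% under step-down. Both respect the 5% limit the plan sets, but step-down uses more of it.
- **The largest gain is a best case.** It needs all three caps to work with effects near 15 hairs. At 22 hairs for all caps the gain is under 1 point per cap. The documents do not state showing all three caps as an objective.
- **40 per arm is the minimum.** The primary analysis is ITT with carry-forward (SAP 8.1), so up to 50 per arm may enter. There single-step already gives 91.6% per cap if imputation does not dilute the effect, which is optimistic.

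Loss of matching simultaneous intervals is usually the main argument for single-step. It carries little weight here, because neither document specifies such intervals.

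**Conclusion.** The point holds as an inexpensive improvement to a valid plan. At 40 evaluable per arm, SD 20 and 15 hairs, step-down Dunnett adds 5.3 points per cap (88.9 − 83.6) and about 13 points for showing all three if every cap works. It adds about 2.3 points per cap if two work and 0.1 point if one works. It adds nothing to the chance of showing at least one cap.

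These figures rest on equal arms, a common SD and no gain from covariates; site terms would alter the df slightly.

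A reader might also infer that step-down repairs the sample size. It does not: 88.9% is still below 90% at 40 per arm, and that only with all three caps working. The shortfall arises because the sample size used an unadjusted 5% test, which is a separate matter.

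**What to change.** Make the change in SAP 8.2 and 10.1 before unblinding; protocol 5.2 can stay as it is.

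- **Rule.** Order the three cap-versus-sham |t| statistics from the primary ANCOVA. Compute two-sided Dunnett p-values for three comparisons (largest |t|), then two, then one, and take the running maximum as the adjusted p-value. Declare a cap superior if its adjusted p-value is at most 0.05 and the difference favours the cap.
- **Scope.** Use the same rule for change in hair count at weeks 8 and 26 and for the rate of change, which SAP 10.2 ties to the primary method.
- **Code.** Revise the example in 10.1, since its LSMEANS line returns single-step p-values.
- **Intervals.** The plan specifies no simultaneous intervals, and step-down has no simple matching set. If any are reported, state that the step-down test decides, because a cap could pass while a single-step Dunnett interval includes zero.

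The cost is SAP wording and a few lines of code, with no extra patients. The SAP should acknowledge that actual false-positive risk moves closer to 5% when some caps are null.

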5.3 Analysis Populations

Participants receive either an active *REVIAN* Cap in three arms or a non-active *REVIAN* Cap (three versions of an active *REVIAN* Cap and one non-active *REVIAN* Cap). The following participant groups or analysis populations will be used to complete the analysis of data:

Intent-to-Treat participant population (ITT): The ITT participant population will include all participants that started a treatment at Baseline. All baseline characteristics, demographics and primary efficacy analyses will be performed on the ITT population.

Per-Protocol participant population (PP): The PP participant population will include all participants in the ITT population with 16-week follow-up data, with no major protocol deviations. The primary and secondary efficacy analyses will be performed on the PP population.

Safety participant population (SAF): The SAF participant population is the same as the ITT population. All safety summaries will be performed on the SAF population.

5.4 Safety Outcomes

Safety outcomes will be determined by evaluating by the type, frequency, severity, and relatedness of adverse events through the 26-weeks timepoint for all participants. All Adverse Events (AEs) will be tabulated and summarized as counts and percentages. AEs will also be cross-tabulated according to the following:

- Severity (Mild, Moderate, Severe)
- Seriousness (Serious, Non-serious)
- Device-Relatedness (Unrelated, Possibly Related, Probably Related, Definite)
- Procedure-Relatedness (Unrelated, Possibly Related, Probably Related, Definite)

In addition, the occurrence of any Unanticipated Adverse Device Effects (UADE) will be listed. The classification of severity, relatedness, and anticipated nature of AEs will be made by the investigator.

5.5 Baseline Variables

Demographic and baseline variables will be summarized. Sample sizes, means, standard deviations and ranges will be presented for all continuous variables.

5.6 Participant Accountability

Lost-to-Follow-Up: The primary analysis will be done on the ITT group. Those participants who withdraw or who are lost (LTFU) after enrollment will be included in the primary analysis using a last observation carried forward (LOCF) approach where the outcome at the most recent visit will be carried forward to all subsequent missing assessment times. Participants without at-least an 8-week visit will have their baseline observation carried forward (BOCF).

5.7 Missing Values

Every effort will be undertaken to fulfill all the requirements of the protocol concerning the collection of data. If participants refuse to return for data collection, but agree to continue in the study, questionnaire data will be collected over the telephone or at home if necessary. Missing values may occur under the following conditions.

- Participants fail improvement and exit the study.
- Participants do not return to the clinic but information regarding REVIAN can be obtained.
- Participants do not return to the clinic but will complete one or more of the questionnaires.
- Participants do not return to the clinic and cannot be contacted.

For other secondary endpoints, analyses will be performed first on all available data with no imputation and additionally with imputed 26-week data.

5.8 Follow-Up and Reporting

All participants enrolled and devices used in the clinical investigation will be accounted for in the final report. All reasons for exclusion from analysis will be carefully documented. Similarly, for all participants and devices included in an analysis population, the measurements of all important variables must be accounted for at all relevant time points. Additional information that is available on participants screened for entry but not enrolled will also be summarized.

Participants lost to follow-up or withdrawn from the study will be identified and a descriptive analysis of them provided, including the reasons for their loss to follow-up and known treatment outcome.

For participants with device failures, data up to the time of the participant's last visit will be pooled with all other participants and analyzed on a per protocol (PP) basis.

5.9 Protocol Deviations

A protocol deviation is defined as an event where the clinical Investigator or site personnel did not conduct the study according to the Investigational Plan or the Investigator Agreement.

Investigators are required to obtain prior approval from study management before deviating from the investigational plan or protocol, except where necessary to protect the life or physical wellbeing of a participant in an emergency. Such approval will be documented in writing and maintained in study files. Prior approval is generally not expected in situations where circumstances are beyond the Investigator's control, (e.g., participant did not attend scheduled follow-up visit, blood sample lost by laboratory, etc.); however, the event is still considered a deviation.

Deviations shall be reported to the study sponsor regardless of whether medically justifiable, preapproved, or taken to protect the participant in an emergency. Participant specific deviations will be reported on the Case Report Form. Non-participant specific deviations will be reported to the sponsor in writing. Investigators will also adhere to procedures for reporting study deviations to their IRB/HREC in accordance with their specific IRB/HREC reporting policies and procedures.

GCP regulations require that Investigators maintain accurate, complete and current records, including documents showing the dates and reasons for each deviation from the protocol.

6.0 STUDY MANAGEMENT

6.1 Sponsor Ethical and Regulatory Considerations

As the Sponsor of this clinical study, PhotonMD has the overall responsibility for the conduct of the study, including assurance that the study meets US federal and local regulatory requirements appropriate to the conduct of the study and is conducted according to the Declaration of Helsinki, Protection of Human Volunteers (21 CFR 50), Institutional Review Boards (21 CFR 56), and Obligations of Clinical Investigators (21 CFR 312). PhotonMD will have certain direct responsibilities and may delegate responsibilities to a Contract Research Organization (CRO). The study sponsor will adhere to sponsor general duties as described in ISO 14155:2011, Clinical investigation of medical devices for human subjects – Good clinical practice, and CFR Part 812, 50, 56, 54 and the World Medical Association Declaration of Helsinki.

To maintain confidentiality, all laboratory specimens, evaluation forms, reports and other records will be identified by a unique participant identification code (ID number and participant name code – initials only). All study records will be kept in a locked file cabinet and code sheets linking a participant's name to a participant identification number will be stored separately in another locked file cabinet. Clinical information will not be released without written permission of the participant, except as necessary for monitoring by the FDA. The Investigator must also comply with all applicable privacy regulations (e.g., Health Insurance Portability and Accountability Act of 1996, EU Data Protection Directive 95/46/EC).

General Duties

PhotonMD will ensure that the application is submitted to the appropriate regulatory authorities, obtaining copies of IRB/HREC approvals and ensuring documentation of IRB/HREC approvals prior to the shipping of devices, ensuring proper clinical site monitoring, ensuring participant informed consent is obtained, providing quality data that satisfies regulations and informing the Investigators and IRB/ECs of unanticipated adverse device effects, events, and deviations from the protocol as appropriate.

The investigation must be reviewed and approved by the appropriate IRB/HRECs before participant enrollment may begin. All proposed changes to the investigational plan must be reviewed and approved by PhotonMD. PhotonMD will also obtain any necessary regulatory approval, per local requirements.

Selection of Clinical Sites

The primary requirements of site and Investigator selection and continued participation in the Trial are: adequate experience, commitment to safety, consistency in adherence to the protocol, and participant volume. Participating sites will be screened to ensure they have sufficient numbers of eligible participants who are representative of the target population. Each center must have facilities that are capable of processing participants in the manner prescribed by the protocol.

The study sponsor, PhotonMD, and its designees will select qualified Investigators, ship or deliver devices only to participating Investigators, obtain signed study agreements, and provide Investigators with the information necessary to conduct the study.

Site Training

The training of appropriate clinical site personnel will be the responsibility of the Sponsor or designee. The Investigator is responsible for ensuring that his/her staff conduct the study according to the protocol. To ensure proper device usage, uniform data collection, and protocol compliance, the Sponsor or designee will present a formal training session to study site personnel which will review the instructions for use of the device, the Investigational Plan, instructions on in-hospital data collection, methods for soliciting data from alternative sources, schedules for follow-up with the study site coordinators, and regulatory requirements. Detailed feedback regarding completion of forms will be provided by the Sponsor or designee through the regular site monitoring.

Investigator Training

The Sponsor will provide appropriate Investigator training on the use of the *REVIAN* System, including the mobile app and the *REVIAN* Cap. Training will take place prior to the initiation of the clinical investigation. Training will address topics including indications for use of the device, management of complications, and instructions to participants. Training will be documented for each physician on a training log, signed by both the physician and training representative

Participant Confidentiality

Participant confidentiality will be maintained throughout the clinical study in a way that ensures the information can always be tracked back to the source data. For this purpose, a unique participant identification code (ID number and participant name code) will be used that allows identification of all data reported for each participant.

Data relating to the study might be made available to third parties (for example in case of an audit performed by regulatory authorities) provided the data are treated confidentially and that the participant's privacy is guaranteed.

Record Retention

PhotonMD will maintain copies of correspondence, data, shipment of devices, adverse device effects, Investigator agreements and other records related to the clinical trial. All study records and reports will remain on file at the sites for a minimum of 2 years after completion of the Study, and will further be retained in accordance with local guidelines as identified in the clinical study agreement. Study records are to be discarded only upon notification by the study sponsor. The Investigator must contact the study sponsor before the destruction of any records and reports pertaining to the study to ensure they no longer need to be retained. In addition, the sponsor should be contacted if the Investigator plans to leave the investigational site. All required data for this study will be collected on standardized CRFs or an electronic data capture system. All information and data sent to the Sponsor or Contract Research Organizations (CROs) concerning participants or their participation in this study will be considered confidential. All data used in the analysis and reporting of this evaluation will be used in a manner without identifiable reference to the participant. The principal Investigator consents to visits by the staff of the Sponsor and its authorized representatives and the U.S. Food and Drug Administration or any other local governmental body to review the study participants' medical records including any test or laboratory data that might have been recorded on diagnostic tests media (e.g., photographs, etc.).

